# 8.2.2 Safety Analyses

All adverse events (AEs) occurring after initiation of study treatment (treatment emergent AEs) will be summarized by severity, relatedness, overall and treatment group. AEs occurring during the screening period will be summarized separately. All AEs will be classified using the MedDRA dictionary.

All verbatim descriptions will be listed for all AEs, along with information regarding onset, duration, severity, relationship to treatment, and action taken.

Serious adverse events will be summarized and presented according to nature, time to onset, duration, relationship to treatment and outcome.

Fisher's Exact tests will be carried out to compare each preferred term between treatment groups. Testing will be carried out at a two-sided alpha level of 0.05.

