## 2. Study Objectives and Purpose

The purpose of this study is to investigate the efficacy of 3MTM Dry Mouth Moisturizing Spray to reduce symptoms of dry mouth for up to 4 hours and after 7 days of use. In addition, this study aims to support comparative claims.

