## 3.2 Primary and Secondary Endpoints

The primary endpoint of this study is reduction in mouth dryness at 15 minutes after 1 dose of 3MTM Dry Mouth Moisturizing Spray.

We hypothesize that the use of 3MTM Dry Mouth Moisturizing Spray will be non-inferior to GSK Biotène® Moisturizing Mouth Spray (Biotene) in alleviating mouth

Page 9 of 36 Status: Release

Version: 3 Issue Date: 07/11/2019 03:08:44 PM CDT

[name]

dryness as assessed by the Visual Analog Scale for the duration of 15 minutes after 1 dose.

The secondary endpoints are to:

- Mouth dryness evaluated using a Visual Analog Scale, at 5-, 30-, 60-, 120and 240-minutes post 1 dose of use to determine whether 3MTM Dry Mouth Moisturizing Spray is equally effective to the prototype Biotène® control.
- Evaluate the clinical safety of the 3M Dry Mouth Moisturizing Spray.
- Determine product usability, acceptability and preference using patient questionnaires.
- Compare 3MTM Dry Mouth Moisturizing Spray to Biotene® and water.

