## 7. Assessment of Safety

## 7.1 Safety Parameters

The principal measures of safety will be the incidence of adverse events reported during the study.

Only treatment-emergent adverse event will be reported.

Examples of anticipated adverse events are:

- Temporary and mild, mouth or tongue sensations such as:
  - Numbness
  - o Burning sensation
  - o Tingling sensations
  - Taste alteration
- Superficial tissue sloughing on the inner surface of the cheeks, which is transient and painless.

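### The only between-product safety inference is an unpaired Fisher test per preferred term: it ignores the crossover, gives no interval, and has low power for modest differences, so a non-significant result is not evidence of comparable safety

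*Combined protocol and SAP*

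**What the plan says.** Section 3.2 lists safety among the secondary endpoints: "Evaluate the clinical safety of the 3M Dry Mouth Moisturizing Spray". Section 7.1 sets the measure: "The principal measures of safety will be the incidence of adverse events reported during the study". It then gives examples of anticipated events, introduced by "Temporary and mild, mouth or tongue sensations such as" and followed by numbness, burning, tingling and taste alteration, with superficial sloughing as a further item. The risk list in section 1.3 overlaps with these and adds stinging, erythema and edema.

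For the analysis, section 8.2.2 says that treatment-emergent events "will be summarized by severity, relatedness, overall and treatment group", and that "All AEs will be classified using the MedDRA dictionary". Verbatim listings and separate summaries of serious events are also planned. The one inferential step is "Fisher's Exact tests will be carried out to compare each preferred term between treatment groups", with the level given as "Testing will be carried out at a two-sided alpha level of 0.05". No risk difference, confidence interval, grouped oral term or safety margin is specified.

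Section 3.3 describes a two-period crossover (AB or BA), so each subject is to receive both sprays. Section 8.3 sizes the trial on the VAS alone. Section 2 adds: "In addition, this study aims to support comparative claims".

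**The concern.** Three features of the safety comparison work against it.

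- **Pairing.** Fisher's exact test compares independent groups. Here the same people supply both counts. A subject who reacts to both sprays carries no information about the difference, yet such subjects raise both counts and blur the comparison.
- **No estimate.** A p-value above 0.05 does not say how large a difference is still compatible with the data. In a trial of 40 that is the main thing a reader needs to know.
- **Unit of test.** Testing each preferred term can divide one pattern of local irritation among several small counts. How the events would be coded is an inference from the separate listing in section 7.1; the documents do not settle it.

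At stake is how the safety results will be read. If the experimental spray irritates moderately more often than the comparator, the planned tests will probably all be non-significant, and the plan provides no interval to put that result in proportion.

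**Working it through.** **Inputs.** 33 evaluable subjects, 40 randomized (section 8.3); two-sided 0.05 per preferred term (section 8.2.2); both sprays used by each subject (section 3.3). The documents give no adverse event rates for this trial, so every rate below is assumed and a range is shown.

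**1. The plan's own sizing.** Power of the paired t-test for non-inferiority comes from the noncentral t with ncp = (1.5 − 0.5)/1.5 × √n, one-sided 0.01. This gives 89.9% at n = 32 and 91.0% at n = 33, so 33 is reproduced. Allowing 15% dropout, 33/0.85 = 38.8, that is 39; the plan's 40 is consistent. None of this concerns safety.

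**2. Counts needed for significance on one term.** For x/40 v 0/40 the two-sided Fisher p-value is 2 × C(40,x)/C(80,x).

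- x = 5: p = 0.055
- x = 6: p = 0.026

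Enumeration gives minimum counts of 6 v 0, 8 v 1 and 9 v 2, the same at n = 33.

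**3. Power on one term.** Sum Bin(a; n, pA) × Bin(b; n, pB) over all tables with p ≤ 0.05 and a > b.

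| Assumed rates, A v B | n = 40 | n = 33 |
|---|---|---|
| 10% v 0% | 21% | 11% |
| 15% v 5% | 18% | 12% |
| 20% v 5% | 41% | 29% |
| 15% v 0% | 57% | 37% |
| 20% v 0% | 84% | 67% |

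**4. Effect of the pairing (n = 40).** Exact McNemar uses only subjects who react to one product.

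| Assumed pattern | Fisher | Exact McNemar |
|---|---|---|
| 20% v 5%, occurrences independent within subject | 41% | 39% |
| 5% react to both, 15% to A only (20% v 5%) | 37% | 57% |
| 10% react to both, 15% to A only (25% v 10%) | 25% | 57% |

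With independent occurrences the two tests perform alike. When some subjects react to both sprays, the paired test is clearly better.

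**5. Effect of grouping (n = 40).** Take five local effects at 5% on A and 1% on B. Power per term is about 0.95%, so under independence the chance that any of the five is significant is 1 − (1 − 0.0095)^5, about 5%. For the group, the proportion with at least one effect is 1 − (1 − p)^5 under independence. Under overlap it comes from equally correlated latent normals.

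| Overlap between effects | Group rate, A v B | Pooled Fisher power |
|---|---|---|
| Independent | 22.6% v 4.9% | 55% |
| Latent correlation 0.5 | 16.6% v 4.0% | 31% |
| Latent correlation 0.8 | 11.7% v 2.8% | 14% |

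**6. What an interval would add.** Newcombe 95% intervals for independent proportions at n = 40 serve as illustration; the paired version depends on the concordant pairs.

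- 0 v 0 events: −8.8 to +8.8 percentage points.
- 4 v 0 events: difference +10.0 points (−0.6 to +23.1), Fisher p = 0.116. The test alone would report only non-significance.

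**The case against.** A reader might infer that a null result is almost certain and uninformative. The documents do not support that. Power depends on rates they do not give, and it reaches 57% at 15% v 0% and 84% at 20% v 0% on a single term. A null result makes very large differences unlikely. The planned summaries of incidence, severity, relatedness and serious events are informative in their own right.

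Nor does any section say that p > 0.05 will be read as safe or comparable. The safety objective in section 3.2 is not worded as a comparison, and the sentence on comparative claims in section 2 follows one about symptom relief; nothing ties it to safety.

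Grouping is not a guaranteed gain either. The more the effects occur in the same subjects, the smaller the benefit, and with complete overlap there is none. Finally, the risk appears low: section 1.5 describes a non-significant-risk device with no adverse events in two taste studies, and section 1.3 says all ingredients are used in food. Descriptive tables with exploratory tests are ordinary in such a setting.

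These points limit the strength and the urgency of the criticism. They do not answer the mismatch between an independent-groups test and a crossover, or the absence of any interval. Low expected rates are also where the per-term test is weakest.

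**Conclusion.** The point holds in a limited form. The only between-product safety inference ignores the pairing, provides no estimate or interval, and has 18% to 41% power at n = 40 for differences of 10 to 15 percentage points at the lower rates examined (10% v 0%, 15% v 5%, 20% v 5%). With 33 subjects the range is 11% to 29%. A non-significant term is then the likely outcome and cannot stand as evidence of comparable safety.

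All of this rests on assumed event rates. The gain from pairing rests on how many subjects react to both sprays, and the gain from grouping on how far the effects overlap. It would be wrong to conclude that a paired test would change nothing; that is true only when reactions to the two sprays are unrelated within subjects. The primary VAS analysis is unaffected.

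**What to change.** In section 8.2.2, replace the per-term Fisher tests with the within-subject A − B difference in the proportion of subjects affected and its two-sided 95% confidence interval, using a method for paired proportions. If a p-value is wanted, use exact McNemar. Report this for:

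- any adverse event; and
- one prespecified group of local oral effects drawn from both section 7.1 and the section 1.3 risk list: numbness or paresthesia, burning or stinging, tingling, taste alteration, sloughing, erythema and edema.

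Show individual preferred terms descriptively, and state that non-significance will not be reported as comparable safety. The interval is an estimate, not a formal test: a claim of comparable safety would also need a prespecified margin, which the documents do not contain. Fix the list of grouped effects before the data are seen, so that the grouping cannot be challenged as post hoc.

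The cost is SAP wording and one extra table, with no new data, visits or subjects. The intervals will be wide, and the safety statement may read less favourably than a list of non-significant tests.

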#### 8.3 Sample Size Justification

When the sample size in each group is 33, a paired t-test with a one-sided significance level of 0.01 will have 90% power to reject the null hypothesis that the test is inferior to the standard in favor of the alternative hypothesis that the treatment is non-inferior when the expected mean difference is 0.5, assuming that the non-inferiority margin is 1.5 and the standard deviation of the differences is 1.5. The sample size goal is inflated to 40 to allow for an approximately 15% drop out rate.

Page 30 of 36 Status: Release

Version: 3

Issue Date: 07/11/2019 03:08:44 PM CDT

#### [name]

References: Mouly et al. Drugs Aging 2007; 24(11) and Mouly et al Journal of Clin Psychopharmacology; 27(5) 2007. The former reference documented that the mouth dryness VAS responses at baseline and Day 14 end of study varied with standard deviations of 1.5, which is the basis for the non-inferiority margin of 1.5 chosen. In addition, standard deviations of VAS differences were 0.4 in the latter reference.

- 8.4 Interim Analyses Planned and Criteria for the Termination of the Study There are no interim analyses planned for this study.
- 8.5 Procedures for Accounting for Missing, Unused, and Spurious Data Missing efficacy data will not be imputed. Subjects lost to follow-up or discontinued will not be replaced.
- 8.6 Deviations to Statistical Plan
  Any deviation from the original statistical plan will be described and justified in the final report.

# 9. Monitoring

3M, as sponsor of this study, is responsible for ensuring the proper conduct of the study with regard to protocol adherence and validity of the data recorded on the CRFs. 3M Company uses a risk-based approach to study monitoring. Protocol compliance and source data review will be conducted periodically (e.g., at a minimum of annually) by the assigned CRA. The progress of the study will be monitored by:

- Periodic on-site review
- Review of CRFs and source documents (e.g., patient hospital records, clinical charts, progress/doctor's notes, oral exam results)
- Telephone and email communications as needed

The Investigator will give the 3M study monitor direct access to source documents that support data on the CRFs and make available such records to authorized 3M, quality assurance, IRB, and regulatory personnel for inspection and/or copying.

Note: The Federal Privacy rule (HIPAA) specifically permits the use and disclosure of protected health information "to a person subject to the jurisdiction of the Food and Drug Administration (FDA) [e.g., study sponsor] with respect to an FDA-related product or activity for which that person has responsibility, for the purpose of activities related to the quality, safety, or effectiveness of such FDA-regulated product or activity" [45 CFR 164.512(b)(1)(iii)].

## 10. Quality Control and Quality Assurance

Page 31 of 36 Status: Release

Version: 3

Issue Date: 07/11/2019 03:08:44 PM CDT

[name]

3M is responsible for implementing and maintaining quality assurance and quality control systems through written standard operating procedures (SOPs) to ensure that this study is conducted, and data are generated, documented and reported in compliance with the protocol, GCP and regulations cited in Section 1.5 of this protocol. Study monitoring is carried out to accomplish this.

A qualified individual designated by 3M, to evaluate study conduct and compliance with the protocol, SOPs, GCP and regulatory requirements, will conduct an independent audit of study records. (see ICH GCP Guidance E6 Parts 5.1, 5.19)

#### 11. Ethics

This study will be conducted in accordance with the principles that have their origin in the Declaration of Helsinki, 21 CFR 50 (Informed Consent) and 56 (IRBs).

The study will start only after approval of the protocol and consent form by the IRB. The approval letter or notice must contain the IRB name and identification number, meeting date, and sufficient information to identify the protocol and informed consent by name and number that were reviewed. 3M, prior to study initiation, must receive a copy of the IRB approval letter.

## 12. Data Handling and Record Keeping

## 12.1 Study Personnel

Prior to study initiation, the Investigator must provide 3M with a signed investigator agreement (Statement of Investigator). The agreement contains pertinent investigator information (e.g., qualifications, experience, etc.) as well as the Investigator's commitment to conduct the study according to the protocol and all applicable state and federal regulations.

## 12.2 Pre-Study Documentation Requirements

Prior to study initiation, the Investigator must provide 3M with the following documents:

- Signed Statement of Investigator
- Signed protocol including any amendments in place prior to study initiation
- Curriculum vitae for the Investigator and any co-investigators
- IRB approved consent form.
- HIPPA Authorization form
- IRB study approval letter

3M Confidential
Document Name: CLIN-PROT-ICH-US-11-406546
Clinical and Non-Clinical: CLIN-INDEX-3M-SPON-US-11-050038

Page 32 of 36 Status: Release

Version: 3

Issue Date: 07/11/2019 03:08:44 PM CDT

#### [name]

- IRB name, location and chairperson
- Financial Disclosure documents per 21 CFR 54
- Signed research agreement

## 12.3 Completion of Case Report Forms

3M intends to use electronic data capture (eDC) software for this study. Sites will be trained on the eDC software prior to study enrollment. Each site will be provided with a manual, including instructions on how to complete the CRFs and how to make CRF corrections. Data may be recorded onto data collection sheets (provided by 3M) prior to data entry or may be entered directly into the eDC system. Once the forms are completed, the monitor will review the CRFs to assure accuracy and completeness. The Investigator must review and sign the CRFs for each subject in a timely fashion following completion.

## 12.4 Final Report

3M will prepare and submit a Sponsor Final Report to all reviewing IRBs within 6 months after study completion or termination [see 21 CFR 812.150 (b)(7)].

## 12.5 Records, Reports and Retention Requirements

The Investigator will maintain study records for a minimum of 2 years following completion of the study. Records that must be maintained by the Investigator include, but are not restricted to:

- Signed study protocol, amendments, deviations
- IRB approval of protocol, consent form, authorization form\* waiver of consent and/or authorization and amendments to any of these documents
- Applications to the IRB
- Signed consent and authorization forms
- Case report forms
- Adverse event reports
- Correspondence relating to the study
- Sponsor Final Report

\*Note: "IRBs are not required to review and approve Authorizations under the Privacy Rule. Likewise, IRBs are not required to approve stand-alone Authorizations (i.e. Authorizations that are not incorporated into the informed consent document)". [Institutional Review Boards and the HIPAA Privacy Rule, NIH Publication Number 03-5428, August 2003.] However, IRBs may require approval of the Authorization form at their discretion.

Page 33 of 36 Status: Release

Version: 3

Issue Date: 07/11/2019 03:08:44 PM CDT

[name]

# 13. Appendices

# 13.1 Appendix A - Study Schedule

Visit	Screeni ng/Start of Wash- In	Water Only Evaluati on	Baseline Period 1	End of Treatme nt Period 1	Baseline Period 2	End of Treatme nt Period 2
Subject Meets Inclusion/Exclusion Criteria	X	X	X			
Subject Consented	X					
Subject Authorization	X					
Health History and Changes to Concomitant Medication	X	X	X	X	X	X
Give directions for wash-in/out ≥ 2-day period with water only	X			X		
Distribute oral care supplies (initially or as needed for on-going study)	X			X		
Subject Scheduled for Next Visit; give appropriate directions	X	X	X	X	X	
Subject Completed Wash-In ≥2-day period with Water Only		X			X	
Study Examiner Completes Oral Tissue Exam/Challacombe Scale	X	X	X	X	X	X
Water Only Evaluation – subject swallows 15 ml of water		X				
Subjects Randomized			X			
Salivary Flow Testing			X			
Photographs Taken (Selective)			X	X	X	X
Subjects Complete Dry Mouth Inventory (DMI) prior to dosing		X			X	
Subjects Complete Visual Analog Scale for Mouth Dryness, prior to dosing		X	X	X	X	X
1-2 sprays of sample self -dosed by subject in clinic			X		X	
Subjects Completes Assessment for (post single dose): VAS Form PPAQ form Dry Mouth Relief		X	X		X	
Subject Diary and take-home sample distributed, along with review of directions for take home use			X		X	
Subject Diary Collected				X		X
Experimental Sample Spray Bottle Weighed			X		X	
Experimental Sample Spray Bottle Collected and Weighed				X		X
Adverse Events Assessed		X	X	X	X	X
Usability and Sample Acceptance Questionnaires				X		X
Preference Questionnaire, Study Discontinuation or Completion to be completed at the final visit or at any time the subject is prematurely discontinuation.	uad.					X

to be completed at the final visit or at any time the subject is prematurely discontinued

An unscheduled visit may occur at any time during the study that may require a spray bottle replacement, protocol deviation, adverse event, or oral examination forms to be filled out

[figure not shown]

Care

Version: 3 Issue Date: 07/11/2019 03:08:44 PM CDT

Page 34 of 36 Status: Release

[name]

[figure not shown]

Page 35 of 36 Status: Release

Version: 3

Issue Date: 07/11/2019 03:08:44 PM CDT

[name]

Page 36 of 36 Status: Release

Version: 3

Issue Date: 07/11/2019 03:08:44 PM CDT

[name]

